5.2.4. Sensitivity Estimator

A sensitivity analysis will be performed for primary endpoint (percent change in body weight Week 24) analysis based on modified ITT population (mITT) which will exclude those ITT subjects who are impacted specifically by COVID-19 with missing important study visits and/or discontinuation. The mITT analysis set will be pre-specified before the database lock.

A second sensitivity analysis will be performed to evaluate outlier effect on the primary endpoint. Outliers of percent weight change, which is defined as more than three standard deviations from the mean percent change in body weight from baseline at Week 24, will be excluded from modified ITT population 2 (mITT2) for this analysis.

The same MMRM model described in methods for the primary estimand will be used for the sensitivity analyses described above.

6. EFFICACY/VIROLOGY

6.1. Analysis Specifications

6.1.1. Data Handling Rules

Plasma viral load will be measured using a validated assay at a central laboratory.

Imputation of left censored HIV-1 RNA values: viral load results recorded as "< 20 copies/mL HIV RNA detected", "< 20 copies/mL HIV RNA copies/mL Not Detected" and "NO HIV-1 RNA DETECTED" will be scored at 19.

If there are retesting, repeating the same analysis from same collected sample, last or retested results will be used in analysis.

6.1.2. Virologic Response Definitions

The following imputation methods will be used to calculate virologic response at a given time point addition with applying 50/200 copies/mL as threshold.

Two imputation mechanisms are considered:

- 1. Observed
- 2. FDA Snapshot

The first mechanism, Observed, does not require an imputation procedure. Subjects with a missing value are disregarded in the analysis for that time point.

The second mechanism FDA snapshot approach: The snapshot mechanism is based on the last available plasma HIV-1 RNA level within the window of an analysis time point. This does not necessarily coincide with the HIV-1 RNA assessment with USE = 'Y'.

The snapshot approach will classify subjects into 3 outcome categories: "virologic response", "virologic failure", or "no viral load data in the Week 24 and Week 48 visit windows". Several subcategories of the outcome will also be presented in the analysis and are shown below. The categories below are mutually exclusive such that a subject will be included in one category. If a subject discontinues in the time window

but also has an HIV-RNA value in the time window, then the viral load data will be used to classify the subject's category.

- Virologic response:
 - HIV RNA <50/200 copies/mL in the Week 24 visit window (Week 18-30) and Week 48 visit window (Week 42-54)
- Virologic failure:
 - o HIV RNA ≥50/200 copies/mL in the Week 24 visit window (Week 18-30) and Week 48 visit window (Week 42-54)
 - Virologic failure leading to discontinuation
 - Discontinued due to other reason (i.e., other than AE/death or virologic failure) and last available HIV RNA ≥50/200 copies/mL
- No viral load data in the Week 24 visit window (Week 18-30) and Week 48 visit window (Week 42-54):
 - O Discontinued due to AE/death (subjects will be classified in this category if discontinued prior to Week 24 visit window and Week 48 visit window regardless of HIV RNA level).
 - O Discontinued due to other reason (i.e., other than AE/death or virologic failure) and the last available HIV RNA <50/200 copies/mL (or missing)
 - o Missing data during the Week 24 visit window and Week 48 visit window but on study.

Virologic failure leading to discontinuation will be determined by a medical assessment of the comment fields and other specification reasons for discontinuation to determine if anyone discontinued the trial due to lack of efficacy reasons. Upon further clinical evaluation additional comments or other specification reasons might need to be added, and these will be documented in the DPS. An identified subject will be classified to the snapshot categories as follows:

- Data within window: If an identified subject has HIV RNA data within the window, the HIV RNA data will be used to classify the subject as either at or above the threshold or below the threshold.
- No data within window: If an identified subject does not have HIV RNA data in window, then
 regardless of the last HIV RNA value the subject will be classified as "Virologic failure leading to
 discontinuation".

Virologic response will then be categorized as follows: Yes (virologic response), or No (virologic failure and no viral load data in the Week 24 visit window and Week 48 visit window).

The snapshot approach will also be displayed over time by analysis time points and will follow the same logic as defined above weeks 24 and 48 time point. (Please see Section 2.2. Visit Windows for visit intervals).

Subjects will also be classified as confirmed virologic rebounds if they meet the criteria below:

• Two consecutive HIV RNA ≥200 copies/mL at a scheduled or unscheduled visit after maintaining HIV-1 RNA <50 copies/mL).

6.2. Secondary Endpoints and Analysis Methods

6.2.1. Weeks 24 and 48 Endpoints

In the following, the secondary endpoints at Week 24 are defined for D/C/F/TAF FDC regimen (Immediate Switch Arm) versus INI + TAF/FTC ARV regimen (Delayed Switch Arm), while the secondary endpoints at Week 48 are related to D/C/F/TAF FDC (Immediate Switch Arm) only.

Metabolic:

- Change from Baseline in absolute body weight over time
- Proportion of participants with % change from baseline in body weight >5% over time.
- Proportion of participants with % change from baseline in body weight >3% over time.
- Change from Baseline in BMI over time.
- Change from Baseline in body composition as measured by DEXA scan at Week 24 and Week 48, respectively.
- Change from Baseline in waist circumference over time.
- Change in SBP and DBP from Baseline over time.
- Change from Baseline in fasting lipids over time.
- Change from Baseline in fasting glucose over time.
- Change from Baseline in HOMA-IR at Week 24 and Week 48, respectively.
- Change from Baseline in HbA1c at Week 24 and Week 48, respectively.
- Change from Baseline in leptin and adiponectin at Week 24 and Week 48, respectively.
- Change from Baseline in the proportion of participants with advanced fibrosis according to the NAFLD fibrosis score at Week 24 and Week 48, respectively.
- Change from Baseline in the proportion of participants at high risk of NASH according to the HAIR score at Week 24 and Week 48, respectively.
- Proportion of participants having a dose-reduction or complete withdrawal of anti-hypertensive, anti- hyperglycemic, or lipid lowering agents in the Immediate Switch Arm from Baseline to Week 24 and Week 48, respectively or Delayed Switch Arm from Baseline to Week 24.
- Proportion of participants initiating an anti-hypertensive, anti-hyperglycemic, or lipid lowering agent in the Immediate Switch Arm from Baseline to Week 24 and Week 48, respectively or Delayed Switch Arm from Baseline to Week 24.

Safety:

- Incidence of any Grade AEs (related and not related) through Week 24 and Week 48, respectively.
- Incidence of Grade 3 and 4 AEs (related and not related) through Week 24 and Week 48,

- respectively.
- Incidence of discontinuations due to AEs through Week 24 and Week 48, respectively.
- Incidence of SAEs (related and not related) through Week 24 and Week 48, respectively.
- Change from Baseline in clinical laboratory tests over time.
- Incidence of Grade 3 and 4 laboratory abnormalities over time.

Efficacy:

- Proportion of participants with confirmed virologic rebound through Week 24 and Week 48, respectively.
- Proportion of participants with virologic response (HIV-1 RNA<50 copies/mL) at Week 24 and Week 48, respectively, according to the FDA snapshot algorithm
- Proportion of participants with virologic failure (HIV-1 RNA ≥50 copies/mL) at Week 24 and Week 48, respectively, according to the FDA snapshot algorithm
- Proportion of participants having virologic response (HIV-1 RNA<200 copies/mL) at Week 24 and Week 48, respectively, according to the FDA snapshot algorithm
- Proportion of participants having virologic failure (HIV-1 RNA ≥200 copies/mL) at Week 24 and Week 48, respectively, according to the FDA snapshot algorithm
- Change from Baseline in CD4+ cell count at Week 24 and Week 48 respectively.

Resistance:

- Proportion of participants with baseline DRV, FTC, TFV and INI resistance-associated mutations (RAMs) based on historical genotypes.
- Incidence of observed genotypic and phenotypic ARV resistance for participants meeting HIV-1 RNA rebound criteria through Weeks 24 and 48, respectively.
- Proportion of participants with newly identified post-baseline RAMs and phenotypic resistance compared to pre-baseline resistance tests when available, upon meeting confirmed virologic rebound through Weeks 24 and 48, respectively.

PROs:

- Change from Baseline in the proportion of participants who have bothersome symptoms (scores of 2, 3 or 4) across all items of the HIV-SI at Week 24 and Week 48, respectively.
- Change from Baseline in the proportion of participants who have any symptoms (scores of 1, 2, 3 or 4) across all items of the HIV-SI at Week 24 and Week 48, respectively.
- Association between treatment arm and each bothersome symptom of the HIV-SI adjusting for Baseline variables at Week 24 and Week 48, respectively.
- PGIC and PGIC-S at Week 24 and Week 48, respectively.

Adherence:

• Adherence rates by participant self-report using 4-day recall at Weeks 4, 12, 24, 36 and 48, respectively.

Exploratory:

Exploratory clinical biomarker:

• Change from Baseline in alpha melanocyte-stimulating hormone at Week 24 and Week 48, respectively.

Exploratory PROs:

- Change from Baseline in the scores on the DAILY EATS at Week 24 and Week 48, respectively.
- Change from Baseline in the scores on the BSQ-8D at Week 24 and Week 48, respectively.
- Change from Baseline in the proportion of participants who have no concern (<19), mild concern (19-25), moderate concern (26-33) or marked concern (>33) with their body shape on the BSQ-8D at Week 24 and Week 48, respectively.

6.2.1.1. Consistency of Effect of Baseline to Week 24 (Immediate Switch) versus Week 24 to Week 48 (Delayed Switch)

Metabolic:

- Change in absolute body weight from Baseline to Week 24 (Immediate Switch Arm) compared to the change in absolute body weight from Week 24 to Week 48 (Delayed Switch Arm)
- The proportion of participants having a >5% change in body weight from Baseline to Week 24 (Immediate Switch Arm) compared to the proportion of participants having a >5% change in body weight from Week 24 to Week 48 (Delayed Switch Arm)
- The proportion of participants having a >3% change in body weight from Baseline to Week 24 (Immediate Switch Arm) compared to the proportion of participants having a >3% change in body weight from Week 24 to Week 48 (Delayed Switch Arm)
- Change in BMI from Baseline through Week 24 (Immediate Switch Arm) compared to the change in BMI from Week 24 through Week 48 (Delayed Switch Arm)
- Change in BMI categories from Baseline through Week 24 (Immediate Switch Arm) compared to the change in BMI categories from Week 24 through Week 48 (Delayed Switch Arm)
- Percent change in body weight from Baseline to Week 24 (Immediate Switch Arm) compared to the percent change in body weight from Week 24 to Week 48 (Delayed Switch Arm).
- Percent change in Visceral Adipose Tissue from Baseline to Week 24 (Immediate Switch Arm) compared to the percent change in Visceral Adipose Tissue from Week 24 to Week 48 (Delayed Switch Arm).
- Change in body composition as measured by DEXA from Baseline through Week 24 (Immediate Switch Arm) compared to the change in body composition from Week 24 through Week 48 (Delayed Switch Arm)
- Change in waist circumference from Baseline to Week 24 (Immediate Switch Arm) compared to the change in waist circumference from Week 24 to Week 48 (Delayed Switch Arm)
- The proportion of participants having a waist circumference of > 40 inches for men and > 35 inches for women at Week 24 (Immediate Switch Arm) compared to the proportion of participants having waist circumference of > 40 inches for men and > 35 inches for women at Week 48 (Delayed Switch Arm)
- Change in SBP and DBP from Baseline to Week 24 (Immediate Switch Arm) compared to the change in SBP and DBP from Week 24 to Week 48 (Delayed Switch Arm)
- Change in fasting lipids from Baseline to Week 24 (Immediate Switch Arm) compared to the change in fasting lipids from Week 24 to Week 48 (Delayed Switch Arm)
- Change in fasting glucose from Baseline to Week 24 (Immediate Switch Arm) compared to the change in fasting glucose from Week 24 to Week 48 (Delayed Switch Arm)

- Change in in HOMA-IR from Baseline to Week 24 (Immediate Switch Arm) compared to the change in HOMA-IR from Week 24 to Week 48 (Delayed Switch Arm)
- Change in HbA1c from Baseline to Week 24 (Immediate Switch Arm) compared to the change in HbA1c from Week 24 to Week 48 (Delayed Switch Arm)
- Change in leptin and adiponectin from Baseline to Week 24 (Immediate Switch Arm) compared to the change in leptin and adiponectin from Week 24 to Week 48 (Delayed Switch Arm)
- Change in the proportion of participants from Baseline to Week 24 with advanced fibrosis according to the NAFLD fibrosis score (F0-F1, Indeterminate, and F3-F4) (Immediate Switch Arm) compared to the change in the proportion of participants from Week 24 to Week 48 with advanced fibrosis according to the NAFLD fibrosis score (Delayed Switch Arm)
- Change in the proportion of participants from Baseline to Week 24 at high risk of NASH according to the HAIR score (<2 and ≥2) (Immediate Switch Arm) compared to the change in the proportion of participants from Week 24 to Week 48 at high risk of NASH according to the HAIR score (Delayed Switch Arm)
- Proportion of participants having a dose-reduction or complete withdrawal of anti-hypertensive, anti-hyperglycemic, or lipid lowering agents from Baseline to Week 24 (Immediate Switch Arm) compared to Week 24 to Week 48 (Delayed Switch Arm)
- Proportion of participants starting an anti- hypertensive, anti-hyperglycemic, or lipid lowering agent from Baseline to Week 24 (Immediate Switch Arm) compared to Weeks 24 to Week 48 (Delayed Switch Arm)

Safety:

- Incidence of any Grade AEs (related and not related) through Week 24 (Immediate Switch Arm) compared to the incidence of any grade AEs (related and not related) through Week 48 (Delayed Switch Arm)
- Incidence of Grade 3 and 4 AEs (related and not related) through Week 24 (Immediate Switch Arm) compared to the incidence of Grade 3 and 4 AEs (related and not related) through Week 48 (Delayed Switch Arm)
- Incidence of discontinuations due to AEs through Week 24 (Immediate Switch Arm) compared to discontinuations due to AEs through Week 48 (Delayed Switch Arm)
- Incidence of SAEs (related and not related) through Week 24 (Immediate Switch Arm) compared to Incidence of SAEs (related and not related) through Week 48 (Delayed Switch Arm)
- Change in clinical laboratory tests over time (Baseline to Week 24 for Immediate Switch Arm) compared to the change in clinical laboratory tests over time (Week 24 to Week 48 (Delayed Switch Arm)
- Incidence of Grade 3 and 4 laboratory abnormalities through Week 24 (Immediate Switch Arm) compared to Grade 3 and 4 laboratory abnormalities through Week 48 (Delayed Switch Arm)

Efficacy:

• The proportion of participants with confirmed virologic rebound at Week 24 (Immediate Switch Arm) compared to the proportion of participants with confirmed virologic rebound from Week 24 to Week 48 (Delayed Switch Arm)

- The proportion of participants with virologic response (HIV-1 RNA<50 copies/mL) at Week 24 according to the FDA snapshot algorithm (Immediate Switch Arm) compared to the proportion of participants with virologic response (HIV-1 RNA<50 copies/mL) at Week 48 according to the FDA snapshot algorithm (Delayed Switch Arm)
- The proportion of participants with virologic failure (HIV-1 RNA ≥50 copies/mL) at Week 24 according to the FDA snapshot algorithm (Immediate Switch Arm) compared to the proportion of participants with virologic failure (HIV-1 RNA ≥50 copies/mL) at Week 48 according to the FDA snapshot algorithm (Delayed Switch Arm)
- The proportion of participants having virologic response (HIV-1 RNA<200 copies/mL) at Week 24 according to the FDA snapshot algorithm (Immediate Switch Arm) compared to the proportion of participants having virologic response (HIV-1 RNA<200 copies/mL) at Week 48 according to the FDA snapshot algorithm (Delayed Switch Arm)
- The proportion of participants having virologic failure (HIV-1 RNA ≥200 copies/mL) at Week 24 according to the FDA snapshot algorithm (Immediate Switch Arm) compared to the proportion of participants having virologic failure (HIV-1 RNA ≥200 copies/mL) at Week 48 according to the FDA snapshot algorithm (Delayed Switch Arm)
- Change in CD4+ cell count from Baseline to Week 24 (Immediate Switch Arm) compared to the change in CD4+ cell count from Week 24 to Week 48 (Delayed Switch Arm)

Resistance:

- Incidence of observed genotypic and phenotypic resistance for participants meeting HIV-1 RNA rebound criteria at Week 24 (Immediate Switch Arm) compared to the incidence of observed genotypic and phenotypic resistance for participants meeting HIV-1 RNA rebound criteria from Week 24 to Week 48 (Delayed Switch Arm)
- Proportion of participants with baseline DRV, FTC, TFV and INI RAMs based on historical genotypes
- Proportion of participant with identified post-baseline RAMs and loss of phenotypic susceptibility, when available, upon meeting confirmed virologic rebound at Week 24 (Immediate Switch Arm) compared to proportion of participant with identified post-baseline RAMs and loss of phenotypic susceptibility, when available, upon meeting confirmed virologic rebound from Week 24 to Week 48 (Delayed Switch Arm)

PROs:

- Change in the proportion of participants who have bothersome symptoms (scores of 2, 3 or 4) across all items of the HIV-SI from Baseline to Week 24 (Immediate Switch Arm) compared to the Change in the proportion of participants who have bothersome symptoms (scores of 2, 3 or 4) across all items of the HIV-SI from Week 24 to Week 48 (Delayed Switch Arm)
- Change in the proportion of participants who have any symptoms (scores of 1, 2, 3 or 4) across all items of the HIV-SI from Baseline to Week 24 (Immediate Switch Arm) compared to the change in the proportion of participants who have any symptoms (scores of 1, 2, 3 or 4) across all items of the HIV-SI from Week 24 to Week 48 (Delayed Switch Arm)
- PGIC and PGIC-S at Week 24 (Immediate Switch Arm) and PGIC and PGIC-S at Week 48 (Delayed Switch Arm)

Adherence:

• Adherence rates by participant self-report using 4-day recall at Weeks 12 and 24 (Immediate

Switch Arm) compared to the Adherence rates by participant self- report using 4-day recall at Weeks 36 and 48 (Delayed Switch Arm).

Exploratory:

Exploratory clinical biomarker:

• Change in alpha stimulating-melanocyte hormone from Baseline to Week 24 (Immediate Switch Arm) compared to the change in alpha stimulating melanocyte hormone from Week 24 to Week 48 (Delayed Switch Arm).

Exploratory PROs:

- Change in the scores on the DAILY EATS from Baseline to Week 24 (Immediate Switch Arm) compared to the change in the scores on the DAILY EATS from Week 24 to Week 48 (Delayed Switch Arm)
- Change in the scores on the BSQ-8D from Baseline to Week 24 (Immediate Switch Arm) compared to the change in the scores on the BSQ-8D from Week 24 to Week 48 (Delayed Switch Arm)
- Change in the proportion of participants who have no concern (<19), mild concern (19-25), moderate concern (26-33) or marked concern (>33) with their body shape on the BSQ-8D from Baseline to Week 24 (Immediate Switch Arm) compared to the change in the proportion of participants who have no concern (<19), mild concern (19-25), moderate concern (26-33) or marked concern (>33) with their body shape on the BSQ-8D from Week 24 to Week 48 (Delayed Switch Arm).

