3. OBJECTIVES AND ENDPOINTS

3.1. Week 24 Objectives and Endpoints

Objectives	Endpoints					
Primary						
To assess the percent change in body weight when switching to D/C/F/TAF FDC (Immediate Switch Arm) compared to continuing the current INI + TAF/FTC ARV regimen (Delayed Switch Arm) in virologically-suppressed (HIV-1 RNA <50 copies/mL) HIV-1 infected participants who have experienced rapid and significant body weight gain Secondary	Percent change from Baseline in body weight at Week 24					
Metabolic						
To assess changes in body weight when switching to D/C/F/TAF FDC (Immediate Switch Arm) compared to continuing the current INI + TAF/FTC ARV regimen (Delayed Switch Arm)	 Change from Baseline in absolute body weight at Week 24 Proportion of participants with % change in body weight >3% at Week 24 Proportion of participants with % change in body weight >5% at Week 24 Change from Baseline in BMI at Week 24 					
To assess changes in body composition when switching to D/C/F/TAF FDC (Immediate Switch Arm) compared to continuing the current INI + TAF/FTC ARV regimen (Delayed Switch Arm)	Change from Baseline in body composition as measured by DEXA scan at Week 24 Change from Baseline in waist circumference at Week 24					
To assess change in blood pressure when switching to D/C/F/TAF FDC (Immediate Switch Arm) compared to continuing the current INI + TAF/FTC ARV regimen (Delayed Switch Arm)	Change in SBP and DBP from Baseline at Week 24					
To assess changes in clinical laboratory tests when switching to D/C/F/TAF FDC (Immediate Switch Arm) compared to continuing the current INI + TAF/FTC ARV regimen (Delayed Switch Arm)	 Change from Baseline in fasting lipids at Week 24 Change from Baseline in fasting glucose at Week 24 Change from Baseline in HOMA-IR at Week 24 Change from Baseline in HbA1c at Week 24 Change from Baseline in leptin and adiponectin at Week 24 					
To assess changes in liver biomarkers when switching to D/C/F/TAF FDC (Immediate Switch Arm) compared to continuing the current INI + TAF/FTC ARV regimen (Delayed Switch Arm)	 Change from Baseline in the proportion of participants with advanced fibrosis according to the NAFLD fibrosis score at Week 24 Change from Baseline in the proportion of participants at high risk of NASH according to the HAIR score at Week 24 					

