	Prothrombin time, prolongation (s)	<4.0	4.0-6.0	> 6.0	
	INR	<1.7	1.7-2.3	> 2.3	
	Ascites	None	Mild (or suppressed with medication)	Moderate to severe (or refractory)	
	Hepatic encephalopathy	None	Grade I-II	Grade III-IV	
	Note: If a participant's actual body weight is greater than 20% over their Ideal Body Weight, the participant's Adjusted Body Weight will be used for eGFRcr (Cockcroft-Gault Formula): Ideal Body Weight (IBW): Male: 50kg + 0.9kg x (height(cm) – 152) Female: 45.5kg + 0.9kg x (height(cm) – 152) Adjusted Body Weight: IBW (kg) + 0.4 x (Weight(kg) – IBW (kg))				
HOMA-IR (mg/dL) Non-Alcoholic Fatty Liver	Fasting insulin x Fasting glucose / 405 -1.675 + 0.037 × age (years) + 0.094 × BMI (kg/m²) + 1.13 × IFG/diabetes (yes =				
Disease (NAFLD) Fibrosis Score ¹					
	NAFLD Score <-1.455				
	NAFLD Score $> 1.455 - 0.675 =$ indeterminate score NAFLD Score $> 0.675 =$ F3-F4				
NASH: HAIR Scores ¹²	HAIR score (0–3) is calculated by adding Hypertension = 1, ALT >40 IU =1, and IR index >5.0 = 1				
	A score of ≥2 is high ri	sk for	NASH.		

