1.5. Sample Size Justification

[figure not shown]
Using a T-test with 80% power to detect a difference of 3% at the significance level of 0.05, 2-sided, the sample size per treatment arm is a simple function of effect size (ES): $n_{arm}=16/(ES)^2$. The effect size is the standardized difference: $ES=\Delta/\sigma$, where Δ is the difference between the two arms, and σ^2 is the common variance. Since there was no direct data on the study population to assume the observed difference, Δ =3% is considered a clinical meaningful difference. Internal data from 2 Phase 3 studies^{2, 3} on D/C/F/TAF FDC arm from different HIV patient populations (naive, switch) have shown the %body weight change in the range of 1.5% to 1.8% and standard deviation from 4.0 to 4.6 (Table 1 and Figure 2), resulting a range of ES and corresponding sample size³.

Table 2 Phase 3 Studies on D/C/F/TAF FDC Arm

Study	AMBER D/C/F/TAF arm	EMERALD D/C/F/TAF arm
N % body weight change from baseline at week 24 (SD)	347 1.5 (4.6)	738 1.8 (4.0)
N % body weight change from baseline at week 48 (SD)	340 2.3 (5.0)	728 1.9 (5.1)

(Data on file)

Figure 2: Sample Size Estimation by Treatment Effect Size

Given the uncertainty of either the Δ or the variability, an adaptive unblinded SSR is planned to reestimate the sample size in an IA to ensure adequate power in the hypothesis testing for the primary endpoint using the conditional power approach. An initial sample size of 55 participants per treatment arm (110 participants total) will be used for treatment effect size of 0.54 (ADDPLAN version 6). The IA is planned when approximately 60% of the initial planned 110 participants have completed the Week 12 visit and approximately 30% of participants have completed the Week 24 visit to re-estimate the sample size to ensure adequate power for the hypothesis testing. All cumulative data will be used for the IA. The planned maximum total sample size after SSR is 150 participants. Details for the SSR,

threshold for the conditional power, and protection of overall significance level will be provided in the statistical plan for the IA and monitoring.

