1.6. Randomization and Blinding

1.6.1. Procedures for Randomization

Participants will be randomly assigned to one of two intervention arms based on a computer-generated randomization schedule prepared before the study by or under the supervision of the sponsor. Randomization will be based on a computer-generated schedule, constructed via random permuted blocks to ensure balance across treatment arms in each strata of the stratification factors (sex and race), and prepared before the start of the study by the sponsor.

Central randomization will be implemented in this study. Participants will be randomized in a 1:1 ratio to the Immediate Switch Arm (D/C/F/TAF FDC starting on Day 1 for 48 weeks), or the Delayed Switch Arm (continue current INI + TAF/FTC ARV regimen for 24 weeks then switch to D/C/F/TAF for an additional 24 weeks).

Randomization will be stratified by sex (Male or Female) and race (Black/African American or Non-Black/African American) at Baseline. A maximum enrollment of approximately 70% male participants will be utilized to ensure adequate recruitment of female participants. A maximum enrollment of approximately 70% non-black participants will be utilized to ensure adequate recruitment of diverse races.

The randomization and baseline visit (Day 1) cannot proceed until the investigator has received all results of the screening visit and participant eligibility has been confirmed in interactive web response system (IWRS), which should occur within approximately 30 days after the screening visit (for further details, see Section 8 in Protocol). It is the responsibility of the investigator to ensure that the participant is eligible for the study prior to enrollment. Randomization should be performed on the same day as the baseline visit (Day 1), provided that all screening procedures have been completed and participant eligibility has been confirmed.

The IWRS will assign open-label kit numbers at each study visit. Study drug will be dispensed to the participant in an open-label fashion. The requestor must use his or her own user identification and personal identification number when contacting the IWRS, and then will give the relevant participant details to uniquely identify the participant.

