	NAFLD Score >0.675 = F3-F4
NASH: HAIR Scores ¹¹	HAIR score (0–3) is calculated by adding Hypertension = 1, ALT >40 IU =1, and IR index $>5.0 = 1$
	A score of ≥2 is high risk for NASH.

Approved, Date: 24 March 2023

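### The NAFLD fibrosis score is continuous and already calculated, but the plan reports it only as a proportion or in bands; adding its mean change would gain precision at no data cost.

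*SAP*

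**What the plan says.** Protocol 3.1 sets a secondary metabolic objective: "To assess changes in liver biomarkers when switching to D/C/F/TAF FDC" compared with continuing the current regimen. Two endpoints serve it, one from the NAFLD fibrosis score and one from the HAIR score. SAP 6.2.1 words the first as "Change from Baseline in the proportion of participants with advanced fibrosis according to the NAFLD fibrosis score at Week 24 and Week 48, respectively", and the protocol's Week 24 and Week 48 endpoint lists (1.1, 3.1, 3.2) define it the same way.

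The score is a weighted sum. In Protocol Appendix 2 it starts from a negative constant, minus "1.675 + 0.037 × age (years) + 0.094 × BMI (kg/m²) + 1.13 × IFG/diabetes"; SAP Attachment 2 also shows the AST/ALT, platelet and albumin terms. Attachment 2 gives the cut: "NAFLD Score >0.675 = F3-F4". Protocol 8.1.2 has the score calculated from central laboratory results and clinical status, with no restriction to a subset.

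SAP 6.2.1.1 (consistency of effect) and the baseline subgroups in SAP 2.5 use three bands, which are still categories. On method the documents differ. Protocol 9.4.3.1 applies the primary mixed model to metabolic change-from-baseline endpoints, while SAP 6.2.2.1 makes secondary metabolic endpoints descriptive.

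**The concern.** The objective concerns change, and the score can register change in every participant. Once reduced to a proportion above 0.675, it registers only those who cross that line. A participant who moves from 0.5 to 0.0, or from 1.5 to 0.9, contributes nothing.

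The plan does not do this elsewhere. Weight has absolute change beside the 3% and 5% cuts (SAP 6.2.1). Waist change stands beside the 40 and 35 inch cuts, and BMI change beside BMI categories (SAP 6.2.1.1). BSQ-8D scores stand beside the concern bands (SAP 6.2.1). The two liver scores have only the cut.

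What is at stake is a wide, uninformative interval for the NAFLD endpoint when the same data could give a tighter one.

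**Working it through.** **1. The plan's own figure.** The sample size was set for percent weight change: "Using a T-test with 80% power to detect a difference of 3% at the significance level of 0.05, 2-sided", and "An initial sample size of 55 participants per treatment arm (110 participants total) will be used for treatment effect size of 0.54" (SAP 1.5). The plan's formula gives 16 / 0.54² = 16 / 0.2916 = 54.9, so 55 per arm. An exact two-sample t-test gives 54.8, with 80.1% power at 55. The figure reproduces. The maximum after re-estimation is 150, or 75 per arm. No rate, SD or power is stated for the NAFLD score, so every NAFLD input below is an assumption.

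**2. The proportion, 55 per arm, two-sided 5%.** The half-width of the 95% CI for a difference in Week 24 proportions is 1.96 × √(2p(1−p)/55).

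| Assumed share above 0.675 | Expected per arm | CI half-width (points) | Power to detect a halving (normal; Fisher exact) | n per arm for 80% power |
|---|---|---|---|---|
| 5% | 2.75 | 8 | 10%; 2% | 906 |
| 10% | 5.5 | 11 | 17%; 8% | 435 |
| 15% | 8.25 | 13 | 24%; 15% | 278 |
| 20% | 11 | 15 | 31%; 22% | 199 |

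**3. The mean change.** With SD of change s, the smallest difference detectable with 80% power is s × (1.96 + 0.84) × √(2/55) = 0.534 s. For s from 0.4 to 0.8 this is 0.21 to 0.43 points. The 95% CI half-width is 1.96 × √(2/55) × s, or 0.15 to 0.30 points.

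**4. Both analyses on the same simulated data.** Baseline SD 1.3, SD of change 0.4 to 0.8, 5% to 20% above the cut, 8,000 trials per cell:

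| True shift (points) | Power, change in proportion | Power, mean change |
|---|---|---|
| 0.085 | 3–6% | 8–20% |
| 0.2 | 5–11% | 25–74% |
| 0.3 | 7–19% | 49–97% |
| 0.4 | 9–29% | 74–100% |

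A second set used baseline mean −1.5 to −0.5, SD 1.2 (3% to 16% above the cut) and SD of change 0.4 to 0.7, with the continuous score adjusted for its baseline. A shift of 0.54 SD of change (0.22 to 0.38 points) gave 3–19% as a proportion against 79–81% as a mean. A shift of 0.09 gave 2–6% against 9–22%.

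**5. What the plan's weight difference implies.** Through the BMI term alone, a 3% weight difference moves the score by 0.094 × 0.03 × BMI: 0.076 at BMI 27, 0.090 at BMI 32, 0.102 at BMI 36. Detecting 0.085 points with 80% power as a mean change would need about 350 to 1,400 per arm (s from 0.4 to 0.8).

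**The case against.** Several points on the other side stand and limit the claim.

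- **No test is planned.** Under SAP 6.2.2.1 the endpoint is descriptive and no power is claimed for it. The loss is therefore one of precision; the power figures only show its size.
- **The 80% figure is built in.** An effect size of 0.54 belongs to weight change and was matched to 55 per arm, so applying it to any continuous measure returns about 80%. At BMI 32, producing 0.22 to 0.38 points through BMI alone would take a 7% to 13% weight difference.
- **For a shift from a 3% weight difference alone, the mean is weak too.** Dichotomising is then not the main reason the endpoint is uninformative.
- **Other information exists.** BMI, fasting glucose and HbA1c are continuous endpoints (SAP 6.2.1). AST, ALT, platelets and albumin are summarised as change from baseline (SAP 7.2.2). A reader might infer that nearly all within-person change is discarded; that is not so, although component means do not give the composite.
- **Three bands carry more than one cut.** With the 0.54 SD shift, comparing bands gave about 21% to 52% power in simulation, depending on the assumptions.
- **HAIR also serves the objective.** It too is cut (at 2 or more), but an assumed 40% against 20% would have about 63% power.

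A reader might also infer from the exclusions in Protocol 5.2 that few participants sit near 0.675. Those exclusions cover active viral hepatitis, Child Pugh Class C and transaminases above five times the upper limit. They do not exclude fatty liver or F3-F4 fibrosis, and entry requires weight gain, which raises the score. The share above the cut is unknown.

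**Conclusion.** The point holds as a minor, free improvement. A continuous score is listed only as a proportion or in bands, contrary to the plan's practice for its other cut measures, and this costs precision on the NAFLD part of the liver-biomarker objective.

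With 55 per arm and 3% to 20% assumed above the cut, shifts of 0.2 to 0.4 points would be found with roughly 3–29% power as a proportion and 25–100% as a mean change. For about 0.09 points the figures are 2–6% and 8–22%. All rest on assumed baseline distributions and SDs of change, with no dropout applied. The advantage of the mean holds across the whole range; its size does not.

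A reader might go further and infer that the endpoint has almost no ability to show change, or that the liver objective cannot be answered. The documents do not support that: HAIR, the bands and the component summaries remain, and a very large effect would show even in the proportion. Disappearance from a 15% to 20% rate would be detected with about 85% to 98% power.

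**What to change.** 1. In SAP 6.2.1 and 6.2.1.1, and for consistency in the protocol endpoint lists (1.1, 3.1, 3.2), add change from baseline in the continuous NAFLD fibrosis score at Weeks 24 and 48. In 6.2.1.1 the delayed arm's reference is Week 24.
2. Report the Week 24 between-arm difference with a 95% CI, adjusted for baseline score, as an estimate without a formal test claim.
3. Keep the proportion above 0.675 and the bands as supporting displays.
4. Note beside the table that BMI enters the score with coefficient 0.094, so part of any difference restates the weight result.
5. Reconcile Protocol 9.4.3.1 (primary model for metabolic change-from-baseline endpoints) with SAP 6.2.2.1 (descriptive only), so that the adjusted estimate in step 2 has a stated basis.

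The cost is an endpoint line in each list, one table, and a matching protocol edit so that the two documents agree. No new data are needed and no planned display is lost.
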